The proposed pilot study is a 3 year prospective, randomized, controlled comparison of a single treatment with carbon dioxide laser resurfacing vs. carbon dioxide resurfacing plus autologous epidermal skin graft from a non sun exposed site vs. control. Thirty subjects will receive treatment with each of the modalities on randomly-assigned portions of the treatment area. The primary measures of efficacy are (a) count of the number of actinic keratosis and non melanoma skin cancers, (b) blinded evaluation of severity from standard digital photographs taken before and after the treatments, and (c) change in histology before and after treatment: seen by grading and change of p53 immunostaining. Other study endpoints include time point to the next skin cancer is found in the treatment area, overall clinical appearance, change in mutant P53 of skin samples, and telomere length variability.

Safety measures include (a) pain, (b) scarring, (c) wound healing, (d) and infection

Subjects will be recruited through advertisements posted within the hospital(s), outpatient dermatology clinics and partners electronic mail.

Inclusion criteria

1. Subjects with ages between 18 and 85 years, male or female.
2. Subjects with at least 4 clinically diagnosed AKs per treatment site (up to 200 sq cm), excluding the face.
3. Subjects with history of at least 1 skin cancer within the past year
4. Willingness to participate in the study
5. Informed consent agreement signed by the subject
6. Willingness to follow the treatment schedule and post treatment care requirements
7. Willingness to not use topical or systemic (oral) TREATMENT medications including imiquimod, 5 Fluorouracil, photodynamic therapy, during the treatment period.
8. Has not had treatment for AKs in the treatment area for 4 weeks prior to enrollment

Exclusion criteria

1. Subjects with active skin cancer in the treatment area. Once the non-melanoma skin cancer has been treated, the subject can be immediately enrolled.
2. Infection of the area to be treated
3. An open wound in the area to be treated
4. Presence of suntan in the area to be treated, or active tanning during the study
5. Subjects who have taken medication known to induce photosensitivity in the previous 3 months
6. The patient has any contraindication to use of the CO2 laser
7. Subject is unable to comply with treatment, home care or follow-up visits
8. Subject is pregnant or breast feeding

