Visit	Informed consent	Urine preg test	TX	Photo	# NMSC prior	AK/NMSC count	Biopsy	Overall Appearance scale	AE	Pain scale (VAS)	Patient side effect report	Inv wound assess
Screen	X											
Baseline/TX (Day 0)		X	X	X	X	X	X	X	X			
Day 3				X				X	X	X	X	X
Day 7				X				X	X	X	X	X
Week 4				X		X		X	X	X	X	X
3 month				X		X	X	X	X			X
6 month				X		X		X	X			
1 year				X		X		X	X			
1.5 – 2.5 year visits				X		X			X			
3 year				X		X	X	X	X			

Baseline/Treatment Visit 1(Day 0)

- Baseline and treatment can occur on separate days if necessary. These visits will occur within 2 weeks of each other if done separately**

Part I– Baseline Evaluations (lasting 1 hour).

Part II- Treatment (lasting 2.5 hours)

Part I– Baseline Evaluations (lasting 1 hour).

The investigator will determine the treatment area

- I. AK count within the treatment area**
- II. Confirm no clinically evident NMSC within the treatment area**
- III. Obtain history of number of skin cancers and locations. History will be taken orally from patient but will also review the medical records.**
- IV. Tracings of the treatment area and control site as needed to document**

V. Shave biopsy technique will be used to harvest epidermal biopsies for histologic assessment. 6 scouting biopsies will be done in the treatment area for histologic evaluation and immunostaining

VI. Baseline pre-treatment Photography of treatment area and control site

Shave biopsy for histology

Area will be prepped with alcohol swab, injected with Lidocaine 1% with or without epinephrine. Shave biopsy will be performed with a dermablade. Tissue samples will be taken to the lab and processed for immunostaining of p53 and PCR to determine telomere length. A portion will be frozen and backed for PCR analysis at the end of the study.

Part II- Treatment (lasting 2.5 hours)

- I) Urine pregnancy test for female not yet in menopause
- II) Subject will receive laser treatment to the treatment area. Topical anesthesia will be applied for 1 hour prior to the laser treatment.
- III) Epidermal suction blister graft harvest from donor site and application on randomized treatment area
- IV) Adverse event evaluation
- V) Patient assessments: pain

Procedures in more detail

Laser treatment

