- II) Exam of the treatment area: AK count, evaluate for clinically appearing NMSC present; evidence of scarring, evidence of infection; evidence of healing . Also will get history from patient: visits to dermatologist? and treatments rendered? Will also review medical records to confirm the history.
- III) 6 scouting epidermal biopsies, using shave biopsy technique (from the treatment area) for histology and immunostaining. Will also bank a portion for PCR at the end of the study.
- IV) Adverse event evaluation
- V) Investigator assessments: wound assessment, overall clinical appearance

Follow-up Visits(6 months, 1 year, 1.5 year, 2 year, 2.5 year) (lasting 30 minutes each)

- I) Photography
- II) Exam of the treatment area: AK count, evaluate for clinically appearing NMSC present; evidence of scarring, evidence of infection; evidence of healing . Also will get history from patient: visits to dermatologist? and treatments rendered? Will also review medical records to confirm the history.
- III) Adverse event evaluation
- IV) Investigator assessments: overall clinical appearance

End of Study visit (3 year) (lasting 1.5 hours)

Patients will exit the study after 3 years

- II) Photography
- III) Exam of the treatment area: AK count, evaluate for clinically appearing NMSC present; evidence of scarring, evidence of infection; evidence of healing . Also will get history from patient: visits to dermatologist? and treatments rendered? Will also review medical records to confirm the history

- IV) **6 scouting epidermal biopsies, using shave biopsy technique (from the treatment area) for histology and immunostaining. Will also bank a portion for PCR at the end of the study.
- V) Adverse event evaluation
- VI) Investigator assessments: overall clinical appearance

** During the course of the study, the subjects will have a total of 18 scouting epidermal biopsies using the shave biopsy technique

Evaluation of Safety and Efficacy

Assessed by investigators (non-blinded) and by blinded evaluators (clinical photographs), periodically for 3 years after a single treatment session.

Reported by the Patients

Specific form is attached.

I. Side effects reported by the patient:

To assess major and minor side-effects, patients will be asked for each treatment site to fill in the following sentence for each test site: **“The side effects I experienced after the treatment were:”** E.G.

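### At baseline the six shave biopsies are listed before the photographs, the reverse of Month 3 and Year 3, so the pre-treatment image for primary measure (b) may show fresh wounds

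*Protocol*

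**What the plan says.** Part I (Baseline Evaluations) of the Baseline/Treatment Visit is a numbered list. Item I is "AK count within the treatment area", item IV the tracings, and item V the biopsies: "6 scouting biopsies will be done in the treatment area for histologic evaluation and immunostaining". Item VI follows: "Baseline pre-treatment Photography of treatment area and control site". Baseline and treatment may fall on different days: "These visits will occur within 2 weeks of each other if done separately".

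The Month 3 list gives photography as item I and the biopsies as item III; the End of Study list gives photography as item II and the biopsies as item IV. Both describe the biopsies in the same words: "6 scouting epidermal biopsies, using shave biopsy technique (from the treatment area) for histology and immunostaining". The total is stated too: "During the course of the study, the subjects will have a total of 18 scouting epidermal biopsies using the shave biopsy technique".

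Under Research Design and Methods, primary measure (a) is the "count of the number of actinic keratosis and non melanoma skin cancers", measure (b) is "blinded evaluation of severity from standard digital photographs taken before and after the treatments", and measure (c) is the change in histology and p53 staining. That section randomises the modalities to portions of the treatment area. Part I (items IV and VI) and the Data and Safety Monitoring section name the control apart from the treatment area, and Part II directs the laser at the treatment area.

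**The concern.** Measure (b) compares photographs from before and after treatment, so anything that worsens only the earlier image counts as improvement. The Overall Appearance Scale asks the rater to weigh cosmetic appearance together with photodamage and atypia. The protocol's own table of skin biopsy risks lists swelling, redness, bruising and bleeding as common. A photograph taken just after six shave biopsies can therefore be expected to look different from one taken just before.

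The baseline image cannot be replaced by a clean one. With same-day treatment the skin is ablated soon afterwards; with a gap of up to two weeks, a repeat photograph would show healing biopsy sites.

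If the control is not biopsied, the artefact also differs between the sites being compared, and measure (c) has no untreated tissue to set against the treated tissue.

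**Working it through.** **Stated total.** Biopsies are scheduled at baseline, Month 3 and Year 3. 6 per visit × 3 visits = 18, which agrees with the protocol.

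**Order at each biopsy visit, by list position.**

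| Visit | AK count | Photography | Biopsies |
|---|---|---|---|
| Baseline, Part I | I | VI | V |
| Month 3 | II | I | III |
| Year 3 | III | II | IV |

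Baseline is the only one of the three with biopsy ahead of photography. The AK count precedes biopsy at all three.

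**Where the biopsies fall.** This depends on what 'treatment area' means.

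- *Control outside the treatment area* (Part I, Part II, Data and Safety Monitoring): 18 biopsies in treated skin and 0 in the control. No control biopsy is named anywhere.
- *Control is one of the randomised portions of the treatment area* (Research Design and Methods): an even split would be 6 / 3 = 2 per portion per visit. No allocation rule is given, so an even split is not assured. Even if it were, the wounds would still be in the baseline image.

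**Footprint of the wounds.** The protocol gives no biopsy diameter, so I assume 0.4 to 1.0 cm. Area = 6 × π × (d/2)².

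- d = 0.4 cm: 6 × π × 0.04 = 0.75 sq cm
- d = 1.0 cm: 6 × π × 0.25 = 4.71 sq cm

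On the 200 sq cm upper limit in the inclusion criteria this is 0.4% to 2.4% of the field. On an assumed field of 50 sq cm it is 1.5% to 9.4%. These are areas, not rating effects.

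**Could the biopsies also lower AK counts?** For biopsies placed without regard to lesions, with an assumed AK radius of 0.25 cm and field area A, the chance that a given AK is touched is 1 − (1 − π(d/2 + 0.25)²/A)⁶.

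- A = 200 sq cm: 1.9% (d = 0.4 cm) to 5.2% (d = 1.0 cm), or about 0.1 to 0.2 of 4 AKs
- A = 50 sq cm: 7.4% to 19.4%, or about 0.3 to 0.8 of 4 AKs

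Four is the entry minimum per treatment site and serves here only as a reference number. The effect would be large only if biopsies were aimed at AKs, and the protocol states no such targeting.

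**The case against.** **List order is not stated to be the order of performance.** Part II names the laser in the same item as, and ahead of, an anaesthetic applied an hour earlier, and the visit table puts the treatment column before the photograph column. This stands: the wounds in the baseline image are conditional on staff following the list. But nothing tells staff to photograph first, and the two later lists show the opposite order.

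**'Only in treated skin' rests on an undefined term.** This also stands. The AK count uses the same term, so the narrow reading that leaves the control without biopsies also leaves it without a specified count. The term needs defining on either reading.

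**Stronger conclusions a reader might draw, and why they fail.**

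- *Biopsies bias the AK count in favour of treatment.* At baseline the count is listed first and the treated skin is then ablated through the epidermis within 0 to 14 days. At Year 3 the biopsies follow the last count. Only the Month 3 biopsies could affect later counts, and the effect is small unless AKs are targeted. Visible precancers in either site may in any case receive routine treatment, which is recorded.
- *The net effect over three years favours treatment.* Small scars and discoloration are listed as common after biopsy. In treated skin they could lower later ratings, against the baseline artefact.
- *Biopsy marks unblind the rater.* The appearance form already labels its columns by treatment, so the marks add little.
- *The artefact is worth a set number of grades.* The documents give nothing from which to derive one, and raters may discount an obvious wound.

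**Conclusion.** The point holds as a sequencing defect that bears on a primary measure. As listed, baseline is the only biopsy visit at which photographs follow the biopsies. If the list is followed, the pre-treatment image carries up to six fresh wounds that the Month 3 and Year 3 images do not, and improvement on measure (b) can be overstated. If the control also lies outside the treatment area, as most of the text suggests, the artefact affects treated skin only and measure (c) has no control tissue.

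The conclusion rests on two conditions the protocol leaves open: that list order is followed, and, for the asymmetry and the missing control specimen, that the control is separate. The size in rating grades is unknown. The documents do not support a claim that the trial as a whole is tilted towards treatment, or that AK counts are materially affected. The change is still worth making because it is nearly free and a spoiled baseline photograph cannot be recovered.

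**What to change.** 1. Swap items V and VI of Part I, and state that at every visit photographs and AK counts of all three portions (CO2, CO2 plus graft, control) are completed before any biopsy.
2. State whether 'treatment area' includes the control, and use the term that way throughout, including for the AK count.
3. Spread the existing six biopsies per visit as two per portion, under one site-selection rule applied alike in all three, and mark the sites on the tracing.

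AKs found only in a biopsy specimen should not be added to the clinical count: that mixes two methods of detection and could count a lesion twice at the same visit.

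Cost: reordering two steps, one definition and a mark on the tracing. The total is unchanged: 2 per portion × 3 portions × 3 visits = 18. If the six biopsies would otherwise be shared evenly by the two treated portions, each drops from 3 to 2 specimens per visit, or from 9 to 6 over the study. In return, measure (c) has control tissue.

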Provide a brief description of any foreseeable risks and discomforts to subjects. Include those related to drugs/devices/procedures being studied and/or administered/Performed solely for research purposes. In addition, include psychosocial risks, and risks related to privacy and confidentiality. When applicable, describe risks to a developing fetus or nursing infant.

Foreseeable Risks and Discomforts of Ablative CO2 laser

	Common	Uncommon
Major:		
1. Severe Pain (Pain 8/10 or higher on VAS scale)		x
2. Blistering (with potential for secondary infection)		x
3. Ulceration (deep erosion, deep wound) with scarring		x
4. Blindness (There is a risk of blindness from the CO2		X

laser. Everyone in the room will wear protective goggles or corneal shields at all times during the treatment to prevent eye injury.)		
Minor:		
1. Mild to Moderate Pain (Pain 1-7/10 on VAS scale) (tenderness) (tingling, stinging, prickling, or burning feeling, tenderness)	x	
Topical anesthesia plus cooling air (Zimmer) will decrease pain during treatment.		
During the treatment we will be asking the patient to rate their level of pain according to the visual analog pain scale that will be provided and explained to them. If at any time during the procedure the patient indicates a pain level of 7 or above based on the visual analog pain scale laser treatments will stop and use intralesional 1% lidocaine for anesthesia in the treatment area		
2. Swelling (edema)	x	
3. Redness (erythema)	x	
4. Crusting (scabbing)	x	
5. Pustulation (weeping skin)	x	
6. Exfoliation (scaling or flaking skin)	x	
7. Itchy Skin	x	
8. Ulceration (erosion)	x	
9. Tanning (pigmentation)< 3 months	x	
10. DISEASE flare		x
11. Hypopigmentation (lightening of the skin)	x	
12. Minor Blistering (vesiculation)		x
13. Wheals		x
14. Bleeding	x	
15. Folliculitis/ acne		x
16. Oozing	x	
17. Dysesthesia (change in sensitivity, numbness)		x
18. Infection: The area may become infected; however, keeping the site clean and using the petroleum ointment should prevent this. If the site does become infected, the patient may need to take oral antibiotics. Signs of infection include redness or swelling lasting longer than 3 days, oozing, or fever. If the patients experience any of		x

these symptoms, they will be instructed to contact the study doctor for immediate evaluation. Oral valacyclovir and dicloxacillin will be given to the patients to prevent the risk of herpes virus related complications.		
19. Milia		X

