If this treatment regimen does decrease the number of future actinic keratosis and non melanoma skin cancers within the treatment area it will provide physicians with another treatment option. A single treatment with a CO2 laser would be much more cost effective than recurrent cryotherapy, biopsies, excisions, etc. The treatment would not only be cost effective but time efficient.

EQUITABLE SELECTION OF SUBJECTS

The risks and benefits of the research must be fairly distributed among the populations that stand to benefit from it. No group of persons, for example, men, women, pregnant women, children, and minorities, should be categorically excluded from the research without a good scientific or ethical reason to do so. Please provide the basis for concluding that the study population is representative of the population that stands to potentially benefit from this research.

The risks and benefits of the research are fairly distributed among the populations that stand to benefit from it. Pregnant or breast feeding women will be excluded because the use of epinephrine in the anesthesia is considered class C by the FDA. In addition, lasers are typically not used in a pregnancy patient. Children will be excluded but it is very unlikely that children develop field cancerization, pre skin cancers, or full blown non melanoma skin cancers. No other group of persons will be categorically excluded from the research.

When people who do not speak English are excluded from participation in the research, provide the scientific rationale for doing so. Individuals who do not speak English should not be denied participation in research simply because it is inconvenient to translate the consent form in different languages and to have an interpreter present.

Individuals who do not speak English will not be denied participation in this research. Translation will be provided if need, with appropriate consent form.

For guidance, refer to the following Partners policy:

Obtaining and Documenting Informed Consent of Subjects who do not Speak English

RECRUITMENT PROCEDURES

Explain in detail the specific methodology that will be used to recruit subjects. Specifically address how, when, where and by whom subjects will be identified and approached about participation. Include any specific recruitment methods used to enhance recruitment of women and minorities.

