Subjects will be recruited through advertisements posted within the hospital(s), outpatient dermatology clinics and partners electronic mail. We feel that recruitment may be augmented if we target private dermatology practices where physicians are currently treating many patients with skin cancers. In this way we hope to tap into a pool of eligible and willing subjects. We also intend to make calls to private practices and meet with the clinicians to explain the study and post study advertisements. The first contact will be made in by the subject in response to the study advertisement. During this first study contact subjects will be informed regarding the goals of the study, inclusion/exclusion criteria, study procedure, potential benefits, risks and duration of the study. Subjects will be asked if they would like a copy of the consent form to read, either through the mail or email. Subjects who meet the inclusion and exclusion criteria and remain interested in the study will be invited for a screening visit. During the screening visit, an investigator will ask the subject a few questions to ensure that inclusion and exclusion criteria are met, and to visually examine the area to be treated.

Provide details of remuneration, when applicable. Even when subjects may derive medical benefit from participation, it is often the case that extra hospital visits, meals at the hospital, parking fees or other inconveniences will result in additional out-of-pocket expenses related to study participation. Investigators may wish to consider providing reimbursement for such expenses when funding is available

The topical anesthesia and study supplies will be purchased the Wellman Center for Photomedicine to be used in this study with departmental discretionary funds. We will reimburse subjects according to the grid below for each visit that they complete. If subjects do not complete all visits, they will be compensated for the visits that they do complete. The compensation for taking part of this study will be paid at the last follow-up visit (#3). Parking vouchers for the hospital garage for all study visits will be given immediately after each study visit or follow-up visit. Clinically, all patients who finish this research may have some benefit of the treatments.

Payment Schedule per visit

Study Events	All patients Payment
Visit Baseline Evaluations/Treatment (Day 0)	\$35
Visit Wound follow up Visits (Day 3, 7 and week 4)	\$20/visit (\$60)

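### The only scheduled pregnancy test comes after the six baseline biopsies, whose anesthetic may contain epinephrine, the protocol's first stated reason for excluding pregnant women

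*Protocol*

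**What the plan says.** Exclusion criterion 8 bars pregnant or breast-feeding subjects. Equitable Selection of Subjects gives two reasons. The first is "Pregnant or breast feeding women will be excluded because the use of epinephrine in the anesthesia is considered class C by the FDA". The second is that "lasers are typically not used in a pregnancy patient".

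The schedule table marks a urine pregnancy test once, in the combined Baseline/TX (Day 0) row. The Screen row is marked for informed consent only. Under Baseline/Treatment Visit 1, the visit is divided into Part I (Baseline Evaluations, 1 hour) and Part II (Treatment, 2.5 hours). The six scouting shave biopsies are Part I, item V. The test, "Urine pregnancy test for female not yet in menopause", is Part II, item I.

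The two parts may be held on different days where this is needed: "These visits will occur within 2 weeks of each other if done separately".

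For the biopsies, the site is "injected with Lidocaine 1% with or without epinephrine". For the laser, Part II specifies topical anesthesia, and the laser risk table adds a rescue step for high pain scores: "use intralesional 1% lidocaine for anesthesia in the treatment area".

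At screening, according to Recruitment Procedures, "an investigator will ask the subject a few questions to ensure that inclusion and exclusion criteria are met", and the area to be treated is inspected.

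**The concern.** A safety test should come before the exposure it guards against. Here the protocol names two exposures that make pregnancy an exclusion, and the single test precedes only one of them. For the other, the protocol relies on what the subject says at screening. That can reveal a known pregnancy but not an unrecognised one. The protocol does not accept self-report as enough before the laser, since it requires a urine test there.

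At stake is the safety of a small subgroup. A positive result in Part II would come after six research biopsies had been taken from a woman whom the protocol meant to exclude. The biopsies serve histology, p53 staining and telomere measurement, and the protocol lists pain, bleeding and a small scar among their common risks.

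**Working it through.** The point turns on the order of procedures, so the check is to set the relevant parts of the protocol side by side. The plan states no figure that needs to be reproduced.

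**Step 1: where epinephrine is named.**

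| Procedure | Part | Anesthesia described | Epinephrine named? |
|---|---|---|---|
| Shave biopsies (6) | I, item V | Injected lidocaine 1% | Yes, as an option |
| CO2 laser | II, item II | Topical, applied for 1 hour beforehand | No |
| Laser rescue for pain | II | Intralesional lidocaine 1% | No |

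The shave biopsy is the only procedure for which the protocol names epinephrine.

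**Step 2: the sequence as written.**

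1. Screening: consent, eligibility questions, visual examination. No test.
2. Part I: counts, history, tracings, six biopsies, photography. No test.
3. A gap of 0 days to 2 weeks.
4. Part II: urine test, then laser, then graft.

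No objective pregnancy test comes before step 2.

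**Step 3: whether the schedule table changes this order.** It does not. Baseline and treatment share one row, so the table fixes no order within the visit. Its columns are not in time order either: TX stands to the left of the photography, AK/NMSC count and biopsy columns, yet the baseline versions of all three belong to Part I, before treatment. Only the division into Part I and Part II sets an order, and it puts the biopsies first.

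**Step 4: size.**

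- Biopsies are taken at baseline, month 3 and year 3: 6 + 6 + 6 = 18. This agrees with the stated total, "the subjects will have a total of 18 scouting epidermal biopsies using the shave biopsy technique".
- Biopsies taken before the only scheduled test: 6 of 18, or one third.
- Delay from injection to test: part of the 1-hour Part I plus any wait on a single-day visit, and up to 2 weeks on a split visit.
- Number of women not yet in menopause among the 30 planned subjects: not given.

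**The case against.** The strongest reply is that the numbered lists record what each part contains and not a strict sequence. Baseline photography, for example, is listed after the biopsies, and the laser item mentions the laser before the topical anesthesia that precedes it. Nothing forbids testing on arrival, and a single-day visit is the default. This has some force for single-day visits: staff could test first, but the text does not ask them to. Loose order within a list does not alter the order between Part I and Part II. On a split visit the test belongs to the treatment day, after the injections.

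A second reply is that the stated reason refers to the anesthesia in general, and the rescue lidocaine might also contain epinephrine. If so, the present test would precede one epinephrine exposure. It would still follow the biopsy injection, where epinephrine is expressly allowed.

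A third is that the chain of conditions is long: a woman not yet in menopause, a pregnancy unknown to her, epinephrine chosen although plain lidocaine complies with the protocol, and no test done first. Pregnancy is also an exclusion criterion checked by questioning, and the investigator may exclude anyone judged unsafe to treat. All of this is true. It limits how often the gap would matter but does not close it, because the choice of epinephrine is not tied to a negative test.

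Finally, the 12 biopsies at month 3 and year 3 have no test at all, which may suggest that the test was meant for the laser alone. That would explain the placement without reconciling it with the epinephrine reason. Those later biopsies fall after entry and are outside this point.

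**Conclusion.** The concern holds. As written, the only objective pregnancy check follows the one procedure for which the protocol names epinephrine, although epinephrine is its first stated reason for the exclusion. The laser is already properly covered.

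The conclusion assumes that Part I precedes Part II, as their names and order indicate, and that epinephrine is actually used at some biopsies. Exposure is therefore possible, not certain. The protocol gives no basis for putting a size on any fetal risk, and none is claimed. No estimate, test or sample-size figure is affected. The change should be made because the gap concerns subject safety and costs very little to close.

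**What to change.** - List the urine test as the first item of Part I, before the biopsies, for women not yet in menopause.
- When Part I and Part II fall on different days, repeat the test before the laser, so that the protection now in place there is kept.
- Split the Day 0 row of the schedule table into a Part I row and a Part II row, so that the table shows the order.

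This means one line moved, one line added and one table row divided. The only burden is one extra urine test for women not yet in menopause whose visits are split. Single-day visits need no extra test, and no visit is added.

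### A randomised three-way comparison is promised, but the procedures randomise only the graft and specify lesion counts and biopsies only for the treatment area, named apart from the control site

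*Protocol*

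**What the plan says.** Specific Aims, aim 2, compares CO2 laser, CO2 laser plus epidermal graft, and a control that receives no intervention. Research Design and Methods calls this a randomised controlled comparison and adds: "Thirty subjects will receive treatment with each of the modalities on randomly-assigned portions of the treatment area". It then says: "The primary measures of efficacy are (a) count of the number of actinic keratosis and non melanoma skin cancers". Measure (b) is a blinded rating of severity from photographs, and measure (c) is change in histology and p53 staining.

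The Baseline/Treatment Visit turns this into steps:

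- Part I opens with "The investigator will determine the treatment area".
- Part I, item I: "AK count within the treatment area".
- Part I, item IV: "Tracings of the treatment area and control site as needed to document". Item VI, on photography, names the same two places.
- Part I, item V: "6 scouting biopsies will be done in the treatment area for histologic evaluation and immunostaining".
- Part II, item II: "Subject will receive laser treatment to the treatment area".
- Part II, item III: "Epidermal suction blister graft harvest from donor site and application on randomized treatment area".

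From week 4 on, the follow-up sections place the lesion examination in the treatment area. The biopsies at month 3 and year 3 are also taken there. The Overall Appearance Scale has a separate column for the control site. Data and Safety Monitoring mentions the treatment area and the control side by side, and says that control sites will also serve for comparison.

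**The concern.** One term seems to have two meanings. In the design paragraph the treatment area is the whole region divided at random among the conditions. In the procedures it is the skin that is lasered, with the control site named next to it. Staff work from the procedures, and those contain no step that assigns the control.

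Aim 2 depends on that control. If the investigator's choice of treatment area settles which skin stays unlasered, a difference between lasered and control skin could reflect that choice as well as the laser. If lesions are not counted and tissue is not taken in the control, two of the primary measures have no control data to compare with. There is a single treatment session, so an analysis plan cannot later restore a random assignment or supply counts and biopsies that were not taken.

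**Working it through.** The Protocol gives no figure on this point to reproduce. The check sets the wording side by side and counts from the schedule.

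**Where randomisation is mentioned.** There are two general statements in Research Design and Methods and one procedural mention, the graft step. The background section agrees with the procedures: the graft covers part of the lasered skin, and no unlasered part is mentioned. No section says how the control site is chosen.

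**Reading A: the control lies inside the treatment area.** This follows the design paragraph. Counts and biopsies would then cover it. All three conditions could be randomised, giving 3! = 6 possible assignments per subject. But the laser step, taken literally, includes the control, which conflicts with aim 2.

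**Reading B: the control lies outside the treatment area.** This follows Part I items IV and VI and Data and Safety Monitoring. The control is then not one of the randomised portions. Only the two laser conditions are randomised, giving 2! = 2 assignments, with the control fixed outside them. If the word modalities in the design paragraph means only the two active treatments, the result is the same: laser versus control has no stated random step.

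**Data specified for the control under reading B**, from the visit schedule:

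- Lesion counts are scheduled at Day 0, week 4, months 3 and 6, and years 1, 1.5, 2, 2.5 and 3, which is 9. The examination wording names the control at none of them: 0 of 9.
- Biopsies: 6 per visit × 3 visits (Day 0, month 3, year 3) = 18, matching the Protocol's own total. The wording places none in the control: 0 of 18.
- Baseline comparability could be checked only in part, from the control photographs and the appearance rating, not from lesion counts or p53 histology.

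**Biopsies per site, assuming equal splits.**

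- Two laser sites only: 6/2 = 3 per site per visit, or 3 × 3 = 9 over the study.
- Three sites: 6/3 = 2 per site per visit, or 2 × 3 = 6 over the study.

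**The case against.** The strongest reply is that the design paragraph already calls the three-way comparison randomised, control included, and that a brief visit checklist need not repeat the allocation. If the treatment area there loosely means all three sites, randomisation stands. The schedule's count and biopsy columns name no area. Data and Safety Monitoring foresees lesions arising in the control and has their treatment recorded, so somebody is expected to look. Six biopsies also divide evenly over three sites.

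Part of this stands. The wording omits the control from counts and biopsies but does not exclude it, so 0 of 9 and 0 of 18 hold only under reading B. The loose reading does not settle the matter, however. The procedures use the same term for what is lasered and set the control site beside it. Even on the loose reading, the laser step needs rewording and no assignment step for the control is given.

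Two stronger inferences are tempting and should not be drawn:

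- **That the control will be lasered.** Aim 2, the separate control site in the procedures and the control column of the appearance scale all speak against it. It is a literal consequence of one reading, not a likely intent.
- **That exactly two of three primary measures lack control data because the appearance scale supplies measure (b).** The Protocol lists overall clinical appearance among its other endpoints and does not say that this scale is measure (b). Its visits are also inconsistent: the schedule marks 8, while the follow-up text adds years 1.5, 2 and 2.5, giving 8 + 3 = 11. No claim about measure (b) is made here.

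**Conclusion.** The point holds as a contradiction between the stated design and the conduct instructions, and it must be fixed. On the reading that the procedures support better, with the control as a separate site, laser versus control has no stated random assignment, and primary measures (a) and (c) are not specified for the control: 0 of 9 counts and 0 of 18 biopsies per subject. On the other reading, those data are covered but the laser step conflicts with aim 2.

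Confidence is high that the sections disagree. The Protocol does not establish that the control was in practice chosen without randomisation or left uncounted; it shows only that, as written, nothing prevents either. The direction and size of any bias cannot be computed from it.

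**What to change.** Reconcile Research Design and Methods, the Baseline/Treatment Visit, the follow-up visit sections and Data and Safety Monitoring on where the control lies, and use one term for the lasered skin and another for the whole study region. To deliver the design that the Protocol itself states:

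1. Outline three comparable sites before treatment, and assign CO2, CO2 plus graft and control to them at random before the laser is used.
2. Word Part II, item II so that it refers only to the two laser sites, in agreement with aim 2.
3. State that AK and NMSC counts are recorded separately for all three sites at baseline and at each count visit.
4. State that the existing six biopsies per visit include the control.

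The cost is revised wording, a three-way allocation list and slightly longer counting. No biopsies are added, but under equal splits each laser site gives 2 instead of 3 per visit (6 instead of 9 over the study), so histology within each laser site is less precise. The revision should also say whether the entry minimum of 4 AKs per treatment site applies to the whole region or to each of the three sites. The first would average 4/3 ≈ 1.3 AKs per site at the minimum, and the second requires at least 3 × 4 = 12 in all.
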